1.3.2. Adult Participants: Groups 1-3: Previously Vaccinated Participants: Dose 1 Schedule

Phase ^v	Screening ^a	Study period					Birth	Follow-up			
Visit number ^b	1	2	3	4	5	6-8*	9	10	11	12 ^{dd}	EE ^c
Visit Timing		Dose 1	Dose 1 + 7d	Dose 1+ 14d	Dose 1 + 28d	Monthly phone calls after Dose 1 + 28 days	Pregnancy completion/ termination	PP 1 + 42d	PP 1 + 6 m	PP 1 + 12 m	Early Exit
Visit Day and (Window)	-28 to 1	D1	D8 (±3d)	D15 (±3d)	D29 (±7d)		PP 1 ^d (+3d)	PP 43 (±14d)	PP 183 (±14d)	PP 366 (±14d)	End of Study
Visit Type	Screening	Vaccination	Safety	Safety	Safety Immuno	Phone Call for Safety follow-up	Safety Immuno	Safety Immuno	Safety Immuno	Safety	Early exit
Informed consent (ICF) ^e	●										
Inclusion/exclusion criteria	●	● ^{1,r}									
Randomization		● ¹									
Demographics ^g	●										
Medical and obstetric history ^h ; pre-pregnancy and prestudy meds	●	● ¹									
History of COVID-19 vaccination ^{aa}	●										
Full physical examination ^h	●	● ¹									●
Obstetric examination ^h	●	● ¹									●
Targeted physical examination ^h			●	●	●		●	●	●	●	
Vital signs including body temperature ^z	●	● ²	●	●	●		●	●	●	●	●
Pulse oximetry ⁱ		● ¹									
Obstetric ultrasound ^k	●	● ¹									●
Nasal swab sample and test for SARS-CoV-2 RNA ^l	● ³	● ^{1,4}									
Pre-vaccination symptoms ^m		● ¹									
eCOA training and set-up ⁿ		● ¹									
Distribution of rulers and thermometers		●									
Distribution of pulse oximeter ^o		●									
Training and distribution: nasal swab kit ^{no}		●									
Symptoms of Infection with Coronavirus-19 (SIC), including highest body temperature measured by the participant (ePROs to be completed by the participant in the eCOA) ^p		● ¹									
Vaccination		●									
30 minutes post-vaccination observation ^q		●									
Solicited AE collection ^r		●	●								
Unsolicited AE collection ^r		●	●	●	●						
Participant reactivity diary review by site staff			● ⁵								
(Suspected) COVID-19 surveillance (symptom check) ^s							-----Continuous-----				
Adverse maternal, fetal outcomes							-----Continuous-----				●
AE/SAE/AESI/MAAE recording ^t							-----Continuous-----				●

Phase ^v	Screening ^a	Study period					Birth	Follow-up			
Visit number ^b	1	2	3	4	5	6-8*	9	10	11	12 ^{dd}	EE ^c
Visit Timing		Dose 1	Dose 1 + 7d	Dose 1+ 14d	Dose 1 + 28d	Monthly phone calls after Dose 1 + 28 days	Pregnancy completion/ termination	PP 1 + 42d	PP 1 + 6 m	PP 1 + 12 m	Early Exit
Visit Day and (Window)	-28 to 1	D1	D8 (±3d)	D15 (±3d)	D29 (±7d)		PP 1 ^d (+3d)	PP 43 (±14d)	PP 183 (±14d)	PP 366 (±14d)	
Visit Type	Screening	Vaccination	Safety	Safety	Safety Immuno	Phone Call for Safety follow-up	Safety Immuno	Safety Immuno	Safety Immuno	Safety	Early exit
Concomitant medications ^u		-----Continuous-----									
Delivery history ^v							●				●
Safety sampling											
Laboratory assessments, ~ 6.5 mL ^j	● [#] (~6.5 mL)	● ¹ (~6.5 mL)	● ¹ (~6.5 mL)	● ^{bb} (~6.5 mL)	● ^{bb} (~6.5 mL)		● ¹ (~6.5 mL)	● ¹ (~6.5 mL)			
Whole blood, 12.5 mL ^w Sample will be separated: Plasma sample, 5 mL ^w Serum, 7.5 mL ^w		● ¹ (5 mL), (7.5 mL)	● ¹ (5 mL), (7.5 mL)		● ¹ (5 mL), (7.5 mL)		● ¹ (5 mL), (7.5 mL)	● ¹ (5 mL), (7.5 mL)			
Other sampling											
Humoral immunogenicity sample (serum) ¹		● ¹ (10 mL)			● ¹ (10 mL)		● ¹ (10 mL)		● ¹ (10 mL)		
N-serology sample		● ¹ (2.5 mL)			● ¹ (2.5 mL)		● ¹ (2.5 mL)		● ¹ (2.5 mL)		
Colostrum and breast milk sample, mL (optional) ¹							● ¹ colostrum 0.5 mL	● ¹ breast milk, ≥5 mL			
Vaccination-related biomarker blood sample (PAXgene [®] tubes, 2.5 mL)		● ¹ (2.5 mL)			● ¹ (2.5 mL)		● ¹ (2.5 mL)				
Cellular immunity (PBMC) blood draw Subset of approximately 25 participants per group, if feasible (optional) ^{cc}		● ¹ (30 mL)			● ¹ (30 mL)		● ¹ (30 mL)				

Monthly phone calls are intended for safety follow up and delivery planning, should start after Day 29 and should continue until birth; #optional laboratory assessments at screening to be done at the discretion of the investigator.

¹ pre dose; ²pre and post dose; ³Screening diagnostic tests for current SARS CoV 2 infection will be performed. SARS CoV 2 test is to be repeated pre vaccination on Day 1 only if the test at screening was not done or was done more than 4 days before the Day 1 visit. if an event is ongoing 7 days post vaccination, the participant should be encouraged to continue filling in the diary until resolution and the rest of the diary may be reviewed again at the next visit.

Footnotes:

- a. Screening can be performed within 28 days prior to the study vaccination or on the day of vaccination. If screening is performed on the day of vaccination (recommended), Visit 1 and Visit 2 will coincide on Day 1. In that case, assessments should only be done once. During the screening, at least, all eligibility criteria must be verified prior to randomization and vaccination.
- b. If allowed by local regulations: study visits may take place at the participant’s home or other location in the event of an ongoing SARS CoV 2 infection; visits can be performed by a phone call or a telemedicine contact; except for vaccination visits, scheduled assessments may be performed by a trained HCP.
- c. For those participants who are unable to continue participation until the end of study visit, but for whom consent is not withdrawn, an early exit visit will be conducted as soon as possible. Participants who wish to withdraw consent from participation in the study will be offered an optional visit for safety follow up. For these participants only the safety assessments of the early exit visit (no blood sampling for immunogenicity) will be performed.

- d. Postpartum (PP) 1 refers to the day of pregnancy completion/termination. Visit 9 (PP 1) should occur on the day of pregnancy completion/termination or within 3 days after pregnancy completion/termination. Assessments collected the day before birth can be used but are preferably collected on the date of birth (for example in case of pre planned cesarian). If the delivery takes place in a hospital where the site staff does not have privileges, it is expected that medical records are collected to collect the applicable protocol required information. Blood samples are not expected in this case.
- e. Signing of the ICF should be done before any study related procedure. The ICF can be signed remotely prior to the Screening Visit. Downloading of an application to the participant's eDevice, to access materials for enrollment and study information, is not considered a study related procedure. By signing the main ICF, consent is also given to follow up the neonates/infants after birth.
- f. Check clinical status again before study vaccination.
- g. Maternal demographic information to be collected at screening includes age, race/ethnicity, and geographical location/residence.
- h. Information to be collected for medical and obstetric history, physical examinations and vital signs is specified in Section 8.2. Only relevant medical history (general and obstetric) is to be collected, in particular: history of congenital abnormalities, history of cancer, history of immunodeficiency or conditions treated with immunomodulators, major psychiatric illness, major cardiovascular or lung diseases, history of an allergy to vaccination, ongoing relevant comorbidities per investigator's judgement, history of any comorbidities known to be associated with an increased risk of progression to severe COVID 19 (see Section 10.9) , and history of hepatitis B or hepatitis C infection.
- i. Baseline pulse oximetry measurements will be used to estimate the amount of oxygen in the blood, low levels may indicate either SARS CoV 2 infection or an underlying medical condition.
- j. For laboratory assessments, including chemistry and hematology assessment of platelet counts (to be done locally within 72 hours of blood collection) see Appendix 2, Table 6 for details. If the outcome from the laboratory assessment shows abnormal results that are considered clinically significant, then additional blood samples could be taken until normalization of the readings, at the discretion of the investigator. Urine dipstick for protein and glucose will be performed at these visits. If urinalysis results are positive additional work up for pre eclampsia or gestational diabetes may be warranted, but do not preclude inclusion in the study.
- k. See Section 8.2.1 for details on obstetric ultrasound. Ultrasound is not required at Visit 2 if screening (Visit 1) ultrasound has been obtained within the past 10 days and there is no other indication for repeating the ultrasound (eg. fetal abnormalities).
- l. Diagnostic molecular RT PCR test for SARS CoV 2 infection will be performed at a local laboratory. For exploratory endpoint purposes, a molecular RT PCR test for SARS CoV 2 infection may be performed at a central laboratory and will not be reported to the sites. Test failures or tests that are indeterminate must be repeated. In case of a positive nasal swab result at screening or D1, an exclusion criterion has been met, and samples will not be shipped to central laboratory.
- m. The investigator must check for acute illness or body temperature $\geq 38.0^{\circ}\text{C}/100.4^{\circ}\text{F}$ at the time of vaccination. If any of these events occur within 24 hours prior to the planned vaccination, the vaccination can be rescheduled in accordance to the protocol's window. For further details refer to Section 5.5.
- n. Participants will complete the reactogenicity diary using the eCOA on their own eDevice (smartphone or tablet) when feasible, also provisioned devices will be available on a limited basis. If a participant is unable to complete the eCOA, a study staff member can collect the information on the participant's behalf as detailed in Section 8.1.2. All eCOA assessment should be conducted/completed before any tests, procedures, or other consultations, in order to avoid influencing participant responses.
- o. At Baseline, all participants will be provided a pulse oximeter (to measure blood oxygen saturation and pulse rate), thermometer and a nasal swab kit to be used in case of a COVID 19 episode (see Section 8.1.2). The pulse oximeter and thermometer for the neonate/infant can also be provided.
- p. The SIC questionnaire asks the participant if she had any of the prespecified signs or symptoms of COVID 19 (see Section 10.8 Appendix 8) during the past 24 hours (including highest temperature in the last 24 hours), and (when applicable) to rate the severity. The baseline SIC questionnaire (Visit 2) must be completed prior to vaccine administration.
- q. Participants will be closely observed at the site for a minimum of 30 minutes post vaccination.
- r. Solicited AEs (reactogenicity) and unsolicited AEs will be assessed from time of vaccination until 7 days post vaccination and 28 post vaccination, respectively.
- s. Participant will be asked at least twice a week, through the eCOA, if they have experienced any new symptoms or health concerns that could be related to infection with SARS CoV 2. Refer to Section 1.3.4 Procedures for Participants with (Suspected) COVID 19. In addition, participants will be asked daily within the 30 day time period post vaccination if they have experienced any health concerns related to suspected AESI's, and if so, participants will be advised to contact the study center. Refer to Section 8.3.6 Adverse Events of Special Interest.
- t. All SAEs related to study procedures or non investigational sponsor products will be reported from the time a signed and dated ICF is obtained until the end of the study/early withdrawal. MAAE are to be reported for all participants from the moment of the vaccination until 6 months after vaccination. MAAEs leading to study discontinuation which are to be reported until completion of the participant's last study related procedure. New onset of chronic diseases will be collected as part of the MAAEs. See Section 8.3.1 for more details.
- u. Refer to Section 6.8 for collection and recording of concomitant therapies
- v. Information to be collected for delivery history.

- w. Blood volume will be divided into plasma and serum as described in the laboratory manual and stored for potential coagulation and/or hematology related testing in a central laboratory (see Section 10.2, Appendix 2, Table 7). Unused samples may be used for immunogenicity testing.
- x. Approximately 0.5 mL of colostrum should be collected within 1 week postpartum and approximately ≥ 5 mL of breast milk around PP43. Collection of breast milk and colostrum is optional. Whether the adult participant is breastfeeding, and until when, will be recorded.
- y. In the situation of a completion/ termination of the pregnancy before the completion of the applicable Study Period visits, PP1 (Visit 9) is to be completed. The participant should then follow the visits scheduled in the 'Study Period' up to visit 5 (meaning all scheduled visits in this period except for the monthly phone calls Visits 6-8) AND the 'Follow up' section of the schedule of activities (Visits 10-12). Additional guidance if the pregnancy is completed/ terminated before the pre partum visits are completed is provided in Appendix 10.13.
- z. Body temperature will be measured preferably via the oral route, or in accordance with the local standard of care.
- aa. Any history of COVID 19 vaccination (name/manufacturer of the vaccine and date of administration) ≥ 4 months prior to the study will be reported in the eCRF.
- bb. Laboratory assessments performed at Visits 4 and 5 are optional. If the outcome from the laboratory assessment at Visit 3 show abnormal results that are considered clinically significant, then an on site visit should be performed. In this case, an additional sample should be taken for further assessment 7 days later and until normalization of the readings, at the discretion of the investigator and targeted physical examinations and vital signs should be collected. If the outcome from the laboratory assessment at Visit 3 show normal results, only a safety phone call is required (no physical examinations and vital signs needed).
- cc. With only 1 participant in this subset at the time of writing this Protocol Amendment 7, PBMC sampling will be removed from the study as of Protocol Amendment 7 approval.
- dd. The Follow up safety assessments for adults at the end of the study visit (no.12) may be performed simultaneously with postnatal (PN 12 months) follow up safety visit (no. 14) as feasible.

AE adverse event; AESI adverse event of special interest; COVID 19 coronavirus disease 2019; d day(s); eCOA electronic clinical outcome assessment; FU follow up; ICF informed consent form; MAAE medically attended adverse event; m months; PBMC peripheral blood mononuclear cell; PP postpartum; SAE serious adverse event; SIC Symptoms of Infection with Coronavirus 19; SARS CoV 2 severe acute respiratory syndrome coronavirus.

1.3.3. Neonate/Infants Schedule

Phase	Birth	Postnatal (PN) Follow-up							
		1	2	3	4	5-7	8	9-13	14 ^u
Visit # ^b	Pregnancy Completion (Birth)	2 Weeks of Age	1 mo	2 mo	3 to 5 mo	6 mo ^{c,t}	7 to 11 mo	12 mo ^t End of Study	Early Exit ^d
Visit Timing	PN 1 (+3d) ^a	PN 14 (± 7 d)	PN 30 (± 7 d)	PN 61 (± 7 d)	PN3 mo to 5 mo (±7 d)	PN 6 mo (±14d)	PN 7 to 11 mo (±7 d)	PN 12 mo (±14d)	
Visit Day and (Window)	Safety and Immuno	Safety	Phone Call for Safety follow up	Safety and Immuno	Monthly Phone Call for Safety follow up	Safety and Immuno	Monthly Phone Call for Safety follow up	Safety	Early Exit
Birth outcome	●								
Neonatal medical history ^e	●								
Adverse neonatal outcome	●								
SAE recording ^f	Continuous								
MAAE recording ^g	Continuous								
Concomitant medication ^h	Continuous								
Physical examination ⁱ	●	●		●		●		●	●
Vital signs and body temperature ^j	●	●		●		●		●	●
Apgar ^k	●								
Blood collection(humoral immunogenicity) ^l	●cord blood only (15 mL)			●3.5mL		●3.5mL			
Vaccination related biomarker blood sample (PAXgene [®] tubes)	●cord blood only (2.5mL)								
Pulse oximetry by site staff ^m	●1								
Distribution of thermometer and pulse oximeter ⁿ	●1								
eCOA training and set up ^p	●1								
PedSIC including body temperature measured by the parent/caregiver. eObsRO to be entered by the parent(s) /caregiver(s) in the eCOA ^q	●								
ASQ 3 ^r				●		●		●	● ^{ss}
(Suspected) COVID 19 surveillance (Pediatric Symptom Check) ^o	Continuous								

Note: “Participant” refers to neonate or infant in this section. 1. Can be completed the day before birth.

Footnotes:

- a. Postnatal (PN) 1 refers to the day of birth. If the delivery takes place in a hospital where the site staff does not have privileges, it is expected that medical records are collected to collect the applicable protocol required information. Blood samples are not expected in this case.

- b. If allowed by local regulations: study visits may take place at the participant's home or other location in the event of ongoing SARS CoV 2 transmission in the area of the participant. ; visits can be performed by a phone call or a telemedicine contact. Scheduled assessments may also be performed by a trained HCP.
- c. At approximately 6 months of age or 28 days after the last routine primary vaccination (dependent on the local primary vaccinations schedule)
- d. For those participants who are unable to continue participation in the study up to Visit 14, but for whom consent is not withdrawn, an early exit visit will be conducted as soon as possible. Parent(s)/caregiver(s) who wish to withdraw consent from participation of the participant in the study will be offered an optional visit for safety follow up for the participant. This includes the safety assessments of the early exit visit. For these participants only the safety assessments of the early exit visit (no blood sampling for immunogenicity) will be performed.
- e. Refer to Section 8.2.6 for assessments to be performed as part of neonatal medical history.
- f. All SAEs related to study procedures or non investigational sponsor products will be reported from birth until the end of the study/early withdrawal. All other SAEs are to be reported from the moment of birth until completion of the participant's last study related procedure.
- g. MAAE are to be reported for all participants from the moment of birth until 6 months of age, except for MAAEs leading to study discontinuation, are to be reported from birth until the participant's last study related procedure. New onset of chronic diseases will be collected as part of the MAAEs
- h. Refer to Section 6.8 for collection and recording of concomitant therapies associated with SAEs and MAAEs.
- i. Refer to Section 8.2.1 for assessments to be performed.
- j. Heart rate, respiratory rate, and body temperature. Vital signs measurements are recommended before blood sampling. Body temperatures will be measured according to the local standard of care (actual routes to be recorded in the eCRF).
- k. The overall Apgar score is required to be documented in the eDC. The Apgar score comprises of the parameters: color, heart rate, reflexes, muscle tone, and respiration that could be entered in the eDC if available (See Section 8.2.1).
- l. Blood sample for humoral immunity also includes sample for previous sero confirmation of SARS CoV 2 infection (antibody).
- m. Baseline pulse oximetry measurements will be used to estimate the amount of oxygen in the blood, with low levels indicative either of SARS CoV 2 infection or an underlying medical condition.
- n. If not given on Day 1, parent(s)/caregiver(s) will be provided with a pulse oximeter (to measure blood oxygen saturation and pulse rate) and thermometer no later than Visit PN 1 (to be used during a COVID 19 episode in the neonate/infant [see Section 1.3.5]).
- o. If a participant develops (suspected) COVID 19, refer to Section 1.3.5. Each parent/caregiver will be asked at least twice a week, through the eCOA, if the participant has experienced any new symptoms or health concerns that could be related to infection with SARS CoV 2. Sites should reach out to a parent/caregiver if the parent/caregiver fails to complete the surveillance question upon any of these reminders. The questionnaire will be accessible on the eCOA platform in between scheduled reminders and parent(s)/caregiver(s) will be encouraged to answer the surveillance question in the eCOA as soon as possible after the onset of COVID 19 like symptoms. Every effort will be made to document the status of all participants that are lost to follow up due to the parent/caregiver not completing the eCOA and for whom hospitalization has not been recorded.
- p. eCOA set up should be done by site staff according to PN1 visit window. Actual training can be completed remotely by the parent(s)/caregiver(s); sites should ensure that parents perform this training no later than on PN14. Parent(s)/caregiver(s) will complete the eCOA using an application on their own eDevice (smartphone or tablet) if their device is compatible with the application. All eCOA assessments should be conducted/completed before any tests, procedures, or other consultations to prevent influencing participant responses. If a parent/caregiver is unable to complete the eCOA, a study staff member can collect information on the participant's behalf as detailed in Section 8.1.2.
- q. The PedSIC questionnaire asks the parent(s)/caregiver(s) if their neonate/infant had any of the prespecified signs or symptoms of COVID 19 during the past 24 hours (including highest temperature in the last 24 hours), and (when applicable) to rate the severity.
- r. Neurodevelopmental status will be measured using the Ages & Stages Questionnaire, 3rd edition (ASQ 3) as outlined in Section 8.2.6.
- s. If Early Exit occurs when the infant is 2, 6 or 12 months old.
- t. The PN 6 mo and PN 12 mo visit may coincide with the PP 6 m and PP 12 m, if feasible to respect the visit windows.
- u. The Follow up safety assessments for adults at the end of the study visit (no.12) may be performed simultaneously with postnatal (PN 12 months) follow up safety visit (no. 14) as feasible.

d days; eCOA electronic clinical outcome assessment; eDC electronic data capture; mo months of age; ObsRO observer reported outcomes; PedSIC Pediatric Symptoms of Infection with Coronavirus 19; PN postnatal; SAE serious adverse event.

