To assess the humoral immune response in peripheral blood of adult participants induced by Ad26.COV2.S administered IM as a 1-dose (5×10^{10} vp) schedule during the 2 nd and/or 3 rd trimester of pregnancy, at all blood collection timepoints.	
 • Serological response to vaccination as measured by ELISA (S-ELISA; EU/mL) and/or equivalent assay, at all blood collection timepoints.
To assess the humoral immune response in peripheral blood of adult participants to Ad26.COV2.S administered IM as a 1-dose (5×10^{10} vp) schedule during the 2 nd and/or 3 rd trimester of pregnancy, 28 days after vaccination.	
 • Serological response to vaccination as measured by VNA titers, 28 days after vaccination.
To evaluate the humoral immune response in adult participants who are vaccine naïve at study entry and receive a booster dose during the study, pre-boost and at selected time points post booster vaccination.	
 • Serological response to vaccination measured by binding (S-ELISA and/or equivalent assay) and/or neutralizing (VNA) antibody titers.
Neonates and Infants	
To assess antibody levels against SARS-CoV-2 in neonates and infants, born to adult participants who have received Ad26.COV2.S during the 2 nd and/or 3 rd trimester of pregnancy, at birth (ie, in cord blood) and at approximately 2 months and 6 months of age.	
 • Serological response to vaccination as measured by ELISA (S-ELISA, EU/mL) and/or equivalent assay, at birth (ie, in cord blood) and at approximately 2 months and 6 months of age.
To assess antibody levels against SARS-CoV-2 in neonates/infants, born to adult participants who have received Ad26.COV2.S during the 2 nd and/or 3 rd trimester of pregnancy, at birth (ie, in cord blood).	
 • Serological response to vaccination as measured by VNA titers at birth (ie, in cord blood).
To assess safety in neonates and infants born to adult participants who have received Ad26.COV2.S, during the 2 nd and/or 3 rd trimester of pregnancy.	
 • SAEs (including Multisystem Inflammatory Syndrome in Children [MIS-C]) and AESIs in neonates and infants from birth approximately 12 months of age. • MAAEs in neonates and infants from birth until 6 months of age. • AEs in neonates/infants leading to study discontinuation from birth until discontinuation.

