
To further explore humoral immune responses in neonates/infants born to participants who have received Ad26.COV2.S during the 2nd and/or 3rd trimester of pregnancy, at all or selected blood collection timepoints.
	
Exploratory analyses may include the following:
 
 • SARS-CoV-2 neutralization as assessed by SARS-CoV-2 neutralization assays VNA. • Adenovirus neutralization as measured by VNA. • Functional and molecular antibody characterization including Fc-mediated viral clearance, avidity, Fc characteristics, immunoglobulin (Ig) subclass and IgG isotype, antibody glycosylation, and assessment of antibody repertoire. • Analysis of antibodies to the spike (S), nucleocapsid (N), and RBD of the SARS-CoV-2 S protein, and surface proteins of other coronaviruses.

	
 • Epitope-specificity characterization of antibodies. • Cytokine profiling: Analysis of cytokines, chemokines, and other proteins of the immune response in the serum or plasma. • Passive transfer: Analysis of immune mediators correlating with protection against experimental SARS-CoV-2 challenge in a suitable animal model. • Analysis of binding and/or neutralizing antibodies against emerging SARS-CoV-2 variants.
To evaluate neurodevelopmental status in neonates and infants.	
 • Summary of developmental outcomes using the Ages & Stages Questionnaire, 3rd edition (ASQ3) at 2, 6 and 12 months of age.
To explore changes in the SARS-CoV-2 genome	
 • Identification of SARS-CoV-2 variants by sequencing of nasal swabs samples (as available)

Refer to Section 8 for evaluations related to endpoints.

HYPOTHESIS

No formal statistical hypothesis is to be tested. The study is designed to provide descriptive information regarding the safety, pregnancy outcomes, and immunogenicity of Ad26.COVID.S in adult participants in the 2nd and/or 3rd trimester of pregnancy, as well as the safety and outcomes of neonates/infants.

The study will provide descriptive information regarding the safety and immunogenicity of Ad26.COVID.S administered as a booster dose in participants who had previously received a COVID-19 vaccine and in those that were vaccine naïve at study entry and receive a booster dose during the study.

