The total blood volume to be collected from infants is considered to be acceptable according to guidelines (EU 2008, Howie 2011, Peplow 2019, US HHS 2019) and will not exceed 3.5 mL per blood draw for infants ≤ 6 months of age. Except cord blood, no blood will be collected from newborns.

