a. Calculated as number of samples multiplied by amount of blood per sample. Repeat or unscheduled samples may be taken for safety reasons or technical issues with the samples.

b. Approximately 15 mL (minimum of 10 mL).

Visit Windows

Visit windows that will be allowed are provided in Section 1.3 and summarized below. The participant should be encouraged to come on the day planned but using the visit window is allowed. The timings of the post-vaccination visits will be determined relative to the actual day of the corresponding vaccination. If a participant misses a vaccination or has a delayed vaccination, the post-vaccination visits will be calculated from the imputative vaccination date according to protocol.

If a vaccination window is missed, efforts will be made to vaccinate and collect samples from the participant, even if out of window. The timings of the post-vaccination visits will be determined relative to the actual day of the vaccination, unless they overlap with other scheduled visits. If so, it would be evaluated in a case-by-case basis in which case the sponsor should be contacted, and a case-by-case assessment agreed.

Screening

Screening will be performed within 28 days prior to study vaccination or on the day of vaccination. If screening is performed on the day of vaccination, study visits will be combined (ie, for adult participants, Visits 1 and 2 will occur on Day 1). Screening must be completed, and all eligibility criteria must be fulfilled prior to vaccination. Participants may be rescreened only once (see Section 5.4).

The nasal swab for the RT-PCR test for the presence of SARS-CoV-2 infection must be done within 4 days before vaccination and repeated pre-vaccination if necessary. The study-specific ICF date will be entered into the eCRF.

Sample Collection and Handling

The actual dates and times of sample collection must be recorded in the eCRF or laboratory requisition form. Refer to Section 1.3 for the timing and frequency of all sample collections.

Instructions for the collection, handling, storage, and shipment of samples can be found in the laboratory manual that will be provided. Collection, handling, storage, and shipment of samples must be under the specified, and where applicable, controlled temperature conditions as indicated in the laboratory manual.

Study-Specific Materials

The investigator will be provided with the following supplies:

- Latest version of the Ad26.COVS Investigator Brochure and Addenda

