No formal statistical hypothesis for immunogenicity will be tested. Immunogenicity analyses will be performed on the PPI-NVN set. Analyses may also be performed by vaccination regimen received by the infant's mother during pregnancy and the gestational age at the time of vaccine administration and/or by SARS-CoV-2 baseline serostatus of the infant's mother. The effect of homologous and heterologous boosters on binding antibodies and neutralizing antibody titers in neonates born to previously vaccinated mothers will be evaluated descriptively by group and overall.

A secondary objective of the study is to assess antibody levels against SARS-CoV-2 in neonates/infants born to adult participants who have received Ad26.COVS during the 2nd and/or 3rd trimester of pregnancy, at birth (ie, in cord blood) and at approximately 2 months and 6 months, of age by group and overall, using ELISA (S-ELISA, EU/mL and GMCs).

A further secondary objective of the study is to assess antibody levels against SARS-CoV-2 in neonates/infants born to adult participants who have received Ad26.COVS during the 2nd and/or 3rd trimester of pregnancy, at birth (ie, in cord blood), as measured by VNA titers (antibody GMTs) by group and overall.

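### Footnote c lets infant Visit 8 follow the routine vaccination calendar with no age limits, in conflict with its 6-month ±14-day window and with endpoints defined by age

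*Protocol*

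**What the plan says.** The neonate/infant schedule (Protocol Section 1.3.3) heads Visit 8 as a 6-month visit with a window of ±14 days. Footnote c, attached to that heading, gives the timing as "At approximately 6 months of age or 28 days after the last routine primary vaccination (dependent on the local primary vaccinations schedule". It sets no lower or upper age for the second option.

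The endpoints measured at this visit are tied to age:

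- Section 3 sets the secondary infant S-ELISA endpoint "at birth (ie, in cord blood) and at approximately 2 months and 6 months of age".
- Section 9.2.1 repeats it for the analysis: "at birth (ie, in cord blood) and at approximately 2 months and 6 months, of age by group and overall, using ELISA".
- Section 3 specifies the exploratory neurodevelopmental questionnaire as "3rd edition (ASQ3) at 2, 6 and 12 months of age".

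On windows in general, Section 8 says "Visit windows that will be allowed are provided in Section 1.3 and summarized below". That leads back to Section 1.3, which contains both the ±14-day window and footnote c.

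**The concern.** One visit carries two timing rules, and they usually give different dates. Infants receive no study vaccine, and no infant objective in Section 3 concerns the response to routine vaccines, so the vaccination anchor serves none of the stated endpoints.

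Age at sampling matters because the infant's antibody is largely acquired from the mother and falls over time. If some sites follow the footnote, samples labelled as 6-month may come from infants of different ages, and part of the spread in the 6-month GMC would then reflect local immunisation calendars. In the current schedule Visit 8 is the last planned infant antibody draw, so there is no later timepoint against which to check it. The ASQ-3 at the same visit is also meant for a given age.

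**Working it through.** **Inputs from the protocol.** Visit 8 is at 6 months ±14 days, or at the last routine primary dose plus 28 days (Section 1.3.3). I take 6 months as day 183, the count used for the adult 6-month postpartum visit. The protocol states no sample size, power or antibody half-life for this endpoint, so there is no figure of its own to reproduce beyond the window.

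**Inputs that are assumptions.** These are the infant's age at the last routine dose (14 weeks and 6 months, as examples) and the half-life of maternal antibody (30, 45, 60 and 90 days). None of them is in the documents.

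**Step 1: the window.** 183 − 14 = day 169; 183 + 14 = day 197.

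**Step 2: when the two rules agree.** Visit age under the footnote = age at last dose + 28 days. To land in the window, the last dose must fall between 169 − 28 = day 141 (141/7 = 20.1 weeks) and 197 − 28 = day 169 (169/7 = 24.1 weeks).

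**Step 3: examples outside that range.**

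- Last dose assumed at 14 weeks: 98 + 28 = day 126. That is 57 days before day 183 and 169 − 126 = 43 days outside the window.
- Last dose assumed at 6 months: 183 + 28 = day 211. That is 28 days after day 183 and 211 − 197 = 14 days outside the window.
- Last dose assumed at 5 months: about day 180, inside the window.

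**Step 4: what an age difference does to the level.** With exponential decline, ratio of levels = 2^(age difference / half-life). The two examples lie 211 − 126 = 85 days apart; the window alone spans 28 days.

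| Assumed half-life | Day 126 vs day 211 (85 days) | ±14-day window alone (28 days) |
|---|---|---|
| 30 days | 7.1 | 1.9 |
| 45 days | 3.7 | 1.5 |
| 60 days | 2.7 | 1.4 |
| 90 days | 1.9 | 1.2 |

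**Step 5: from individual levels to the GMC.** The table compares two infants at opposite ends. If a fraction f of infants were sampled at day 126 and the rest at day 183, the GMC would be multiplied by 2^(57f / half-life). Late samples would pull it the other way. The documents give no basis for f, so no GMC shift can be stated.

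**The case against.** The best reply is that the ±14-day window still binds and footnote c operates inside it. The window stands in the same column. Footnote t, on the same visit, allows it to coincide with the mother's visit only where the windows can be respected. The visit order also fits a 6-month visit: at day 126, Visit 8 would come before the 5-month phone call, and at day 211 it would run into the 7-month call. On the late side, Section 4.1.1 says the infant draw "will not exceed 3.5 mL per blood draw for infants ≤ 6 months of age", which does not cover a seven-month-old. This reading is reasonable, but the protocol never states it. The footnote joins the two anchors with a plain alternative and carries no proviso like the one in footnote t.

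The consequences are also limited. Section 9.2.1 says "No formal statistical hypothesis for immunogenicity will be tested", the endpoint is secondary, and the ASQ-3 is exploratory. Section 8 requires that "The actual dates and times of sample collection must be recorded in the eCRF or laboratory requisition form", and Section 6.8 has all infant vaccines captured, so age at sampling can be derived. This stands and lowers the weight of the point. It does not supply a 6-month value for an infant sampled at another age.

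Finally, an anchor that serves no endpoint is not an error in itself. It may help sites combine the visit with a vaccination check.

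**Conclusion.** The conflict is real: an unbounded alternative anchor sits beside a ±14-day window and age-defined endpoints, with no rule of precedence. It may place samples well outside the window, since the two rules agree only for a last dose at about 20 to 24 weeks. The possible spread between extreme infants, about 7.1- to 1.9-fold, exceeds the 1.9- to 1.2-fold that the window alone permits at the same half-lives. All of these ratios rest on assumed half-lives, and the first also on assumed calendars.

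Three stronger readings go beyond the documents. A reader might infer that the 6-month endpoint does mix infants of about 4 to 7 months; no local calendar is given, and sites may have kept to the window. A reader might take the fold ratios as the error in the GMC; they compare two extreme infants, and the share of infants on each anchor is unknown. A reader might expect bias between study groups; groups are defined by the mother's COVID-19 vaccination history, and nothing shows that this tracks infant immunisation calendars.

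The weight is low to moderate: a contradiction worth removing, in a descriptive secondary endpoint.

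**What to change.** Delete the vaccination anchor from footnote c, so that Visit 8 is at 6 months ±14 days only. Alternatively, keep it and state that it applies only within that window. Report samples already taken outside the window by actual age in days, from the recorded sampling dates, rather than within the 6-month GMC; this rule can sit in the SAP, and its absence from the protocol is not a criticism.

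The cost is one footnote edit and one analysis rule. Some sites lose flexibility to combine the visit with a routine vaccination check. Because enrolled infants continue to be followed after enrollment stops, the change can still help any infant who has not yet reached Visit 8.
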